3.5 Treatments

A total of 140 subjects will be randomly assigned in a 1:1 ratio to receive either LE Ophthalmic Gel, 0.5% or Prednisolone Acetate Ophthalmic Suspension, 1%.

4.0 STUDY MATERIALS

4.1 Description of Test Article

Loteprednol Etabonate Ophthalmic Gel, 0.5%, contains the active ingredient loteprednol etabonate 0.5% and the preservative benzalkonium chloride (BAK), 0.003%. It also contains the inactive ingredients glycerin, propylene glycol, sodium chloride, polycarbophil, sodium hydroxide, tyloxapol, edetate disodium dihydrate, boric acid, and water for injection.

4.2 Description of Comparator

Prednisolone Acetate Ophthalmic Suspension, 1% contains the active ingredient prednisolone acetate 1% and the preservative BAK 0.004%. The inactive ingredients are comprised of: boric acid; edetate disodium; hypromellose; polysorbate 80; purified water; sodium bisulfite; sodium chloride; and sodium citrate. The pH during its shelf life ranges from 5.0 - 6.0.

4.3 Instructions for Use and Administration

Following the initial drop administration by the unmasked study personnel at the end of the surgery, either the unmasked designee or the subject's parent/legal guardian will administer 1 to 2 drops of study drug into the study eye once in the evening on the day of surgery and then QID, at approximately four hour intervals, beginning on the morning after surgery. QID dosing will continue until postoperative day 14. Treatment will be tapered from QID to BID during the interval between postoperative days 15 and 21. Treatment will be further tapered from postoperative day 22 until day 28 to QD with the last dose being administered on the day prior to Visit 6 (Postoperative Day 28).

Parents/legal guardians will be trained with regard to the instillation of eye drops prior to administration of the initial dose.

Site personnel will instruct the subject's parent/legal guardian on the proper instillation of their study medication without using the study drug.

Subject's parent/legal guardian will be instructed to return the study drug at Visits 4, 5 and 6 for weighing, and for collection in the original packaging at Visit 6 or early study discontinuation. Both the Investigator and the subjects will be masked to the study drug assignment.

4.3.1 Storage Requirements

All clinical trial material will be stored in an area free of environmental extremes, avoiding excessive heat. Clinical trial material should be stored upright at 15-25°C (59-77°F). A daily temperature log will be maintained at the site. The storage location at the clinical sites will have limited access.

Subject's parent/legal guardian must be instructed regarding proper storage.

4.4 Other Materials

Additional materials (eg, scales) will be provided by the Sponsor, depending on the requirements by the site.

4.5 Packaging and Labeling

The test and control articles will be packaged and labeled in a manner consistent with the study design. All investigational products will be labeled and supplied by the Sponsor. The test article will be manufactured and filled (5-mL) into 10-mL, white, low density polyethylene (LDPE) bottles with pink polypropylene caps by Bausch & Lomb Incorporated (Tampa, FL). The control article, Prednisolone Acetate Ophthalmic Suspension, 1%, will be sourced from readily available commercial supply. The control article will be provided in 10-mL industry standard ophthalmic bottles.

The investigational products will be packaged and labeled in a manner consistent with the study design. Investigational products will be provided in kit boxes (one study kit per subject) each with two dropper bottles containing sufficient doses for duration of treatment. Supply labeling will minimally include the protocol number, kit identification number, product description, directions for use, storage conditions, caution statement, and Sponsor information. Labeling for European sites will follow the requirements of the EU Directive 2001/20/EC (Annex 13).

Subject kit boxes and subject-specific reserve kit boxes will be labeled with a 2-part, tear-off masked label. The left part of the label will remain affixed to the subject kit. Upon dispensing, the right portion of the label, which contains hidden drug information, will be detached and placed in the subject's source document.

Subject supplies will be labeled according to a computer-generated randomization scheme. The medication will be identified as a new drug, limited by federal law, EU Directive, and AP local regulation to investigational use, and appropriately labeled for investigational use for this age group.

4.6 Accountability

The Investigator or designee will be responsible for keeping current and accurate records of the amount of study drug received and dispensed, and its disposition. The study drug must be stored under the appropriate conditions in a secure area and are to be dispensed only to subjects enrolled in the study, in accordance with the conditions specified in this protocol. In order to assess compliance of administration, subject's parent/legal guardian will be instructed to record the date and time of each study drug administration on a diary provided by the Sponsor. Site personnel will dispense diaries and the unmasked designee will weigh study drug (each bottle) before dispensing at Visit 2. Subjects should bring their study diaries and study drug (both bottles) to Visits 3 through 6. Site personnel will review the diaries and the unmasked designee will weigh the study drug (each bottle) at Visits 3 through 6 to assess compliance.

During the course of the study, the Investigator's unmasked designee must maintain an inventory of all study drug, dispensed to or returned by the subject, including subject identifiers.

At time points throughout the study and/or upon completion of the study, the Sponsor/Sponsor's representative will review and verify the Investigator's accountability

records. Following verification, and as directed by the Sponsor, all used, unused and returned product must be returned to the Sponsor at the address provided on the Personnel and Facilities page, or with the Sponsor's permission, disposed of at the site in an appropriate manner.

4.7 Masking/Unmasking

The Investigator, subject/subject's parent/legal guardian, and Sponsor personnel involved in the monitoring or conduct of the study will be masked to the study drug. The randomization list will be produced prior to study enrollment by an unmasked statistician not otherwise involved in the study. Although the test and active comparator bottles will be visibly different, attempts will be made to mask the subjects by removing commercial labeling, replacing with identical investigational labels, and packaging in identical kit boxes. An unmasked designee will be able to view both test and comparator bottles as part of their study activities and are therefore considered as unmasked although the designee will not have access to the randomization code. The unmasked designee will be responsible for instilling the first drop after surgery, and dispensing, weighing and collecting the test articles. The unmasked designee will not be responsible for any study assessments for this study. Site Monitors will be able to monitor subject diaries and accountability records but will not be able to reconcile the bottles in the boxes with the accountability records.

The Investigator must contact the Medical Monitor prior to unmasking of study treatment. In an emergency situation, however, where knowledge of the study treatment is critical to subject safety, the code may be broken. If unmasking is necessary, the masked section of the two-part label, which is placed in the subject's source documentation, can be scratched off to reveal the treatment assignment for that subject.

The Investigator must notify the Medical Monitor and/or Study Manager as soon as possible after unmasking. In addition, the Investigator must record the date, time, and reason for unmasking the study treatment in the source documentation.

4.8 Methods of Assigning Subjects to Treatment Groups

4.8.1 Treatment Allocation

Study drug will be allocated to eligible subjects at Visit 2, which will be the day the subject has undergone routine, uncomplicated surgery for childhood cataract. Each enrolled subject will receive sufficient study drug for the duration of treatment (ie, two bottles). The unmasked designee will dispense the next sequential kit number and administer the first dose after surgery.

4.8.2 Treatment Replacement

Reserve supplies of each subject's study drug (ie, one bottle) will be provided to the Investigators, to be dispensed only if the original subject kit is lost, damaged, or consumed prior to the end of treatment.

4.9 Risk Assessment

Refer to the Investigator's Brochure provided by the Sponsor which includes a summary of data and guidance for the Investigator in regards to the clinical pharmacology and safety profile of LE.

The subject's parent/legal guardian will be informed of any risks in the ICF.

4.10 Selection of Dose

The dose regimen in this study is the same regimen across both treatment groups (ie, 1 to 2 drops of study drug instilled in the study eye, QID, at approximately 4 hour intervals). This regimen was selected for the study based on the dose regimen of the currently marketed *Lotemax* (LE Ophthalmic Gel, 0.5%) and is also the treatment recommended in the Package Insert (PI) and Summary of Product Characteristics (SmPC) of the comparator drug.

Based on the standard of care for the treatment of postoperative inflammation in the US, both treatment groups will be dosed QID for the first 14 days and then tapered to BID from postoperative days 15 through 21 and the further tapered to QD from postoperative day 22 until the day prior to Visit 6 (Postoperative Day 28).

5.0 STUDY METHODS

5.1 Study Visits

Refer to Appendix A for a schedule of visits and parameters and Appendix B for methods of clinical evaluation.

Following identification of a potential subject, the Investigator (or designee) will explain the purpose of the study, procedures, risks/benefits, and subject responsibilities to the potential subject's parent/legal guardian. The subject's/subject's parent/legal guardian willingness and ability to meet the follow-up requirements of the study will be determined. If the subject's parent/legal guardian chooses to participate in the investigation, then the subject's assent (when applicable and according to local regulations) and written informed consent will be obtained. The subject's parent/legal guardian and the person obtaining written consent will sign and date the IRB/EC-approved ICF. The original signed document will be retained in the subject records, and a copy will be provided to the subject's parent/legal guardian. In addition, the applicable privacy regulation requirements must be met.

5.1.1 Visit 1 (Screening, Day -15 ±14 days)

Visit 1 will proceed as follows:

NOTE: All ocular assessments and VA will be performed bilaterally.

- obtain assent (when applicable), written informed consent (US, EU, and AP) and HIPAA authorization (US only)
- determine if the subject meets preliminary eligibility criteria:
 - documentation of demographic information
 - current and relevant medical and ophthalmic history
 - concomitant medications
- if the subject meets the preliminary eligibility criteria, the following assessments will be performed:
 - ocular symptoms

- pediatric visual acuity (VA) testing
- biomicroscopy
- IOP measurement

NOTE: *Measurement of IOP must occur after the assessment of ocular symptoms, VA and biomicroscopy*

NOTE: *Surgery will be scheduled to occur within 29 days of the Screening Visit. Screening and surgery cannot take place on the same day.*

5.1.2 Visit 2 (Surgery/Randomization, Day 0 [within 29 days of screening])

Visit 2 will proceed as follows:

NOTE: *All ocular assessments and VA will be performed bilaterally.*

- record adverse events (AEs) and changes in concomitant medications
- pediatric VA assessment
- biomicroscopy
- IOP measurement
- fundoscopy, if performed during surgery, if not, then perform at Visit 3
- immediately following surgery, determine eligibility

NOTE: *Subjects who, in the Investigator's opinion, have surgical complications such that it is not in their best interest to continue in the study are considered screen failures and will not be randomized into the trial.*

If during the surgery it is determined that additional manipulations, such as pupil stretching or the use of iris hooks are required, it is left to the Investigator's discretion whether or not it is safe to randomize the subject into the trial.

At the conclusion of the surgery, no subconjunctival or intracameral steroid injections are permitted. If a steroid injection is deemed necessary by the Investigator, the subject cannot be randomized and is considered a screen failure.

- randomize eligible subjects by assigning the next sequential subject kit box
- the unmasked designee must weigh both bottles of study drug prior to dispensing
- at the conclusion of surgery, the randomized subject will receive the first dose of study drug from the unmasked designee followed by an antibiotic of the Investigator's choice and an eye patch
- study drug will be dispensed to the subject's parent/legal guardian by the unmasked designee
- a study drug administration diary will be provided to the subject's parent/legal guardian who will be instructed to record the time of each instillation and to bring the diary and study drug (both bottles) to each visit. The subject's parent/legal guardian will be reminded that no other information should be recorded in the diary
- the subject's parent/legal guardian will be trained by site personnel with regard to the correct instillation of eye drops prior to administration of the initial dose at any time at Visit 1 or 2 without using the study drug, but prior to their first instillation of study drug outside of the office. The time and method is left to the Investigator's discretion
- either the unmasked designee or the subject's parent/legal guardian will administer approximately one to two drops of study drug into the lower cul-de-sac of the study

eye in the evening, after removing the patch and before applying the shield, which will cover the study eye overnight

- the subject's parent/legal guardian will proceed with administration of the study drug on the morning of the first postoperative day with QID dosing at approximately four hour intervals, independently of when Visit 3 is scheduled to occur

5.1.3 Visit 3 (Postoperative Day 1; First Calendar Day after Surgery)

At Visit 3, the following assessments will be performed:

NOTE: All ocular assessments and VA will be performed bilaterally.

- AEs and changes in concomitant medications
- the unmasked designee must weigh both bottles of study drug
- ocular symptoms
- pediatric VA
- biomicroscopy
- IOP measurement

NOTE: Measurement of IOP must occur after the assessment of ocular symptoms, VA and biomicroscopy.

NOTE: If, at any time point after surgery, IOP is elevated, treatment or intervention is left to the Investigator's discretion and the subject is to continue the study.

- fundoscopy, if not performed during surgery

NOTE: Topical antibiotic drops should be administered at least 15 minutes AFTER study drug application.

- review and collect study drug administration diary for compliance. Instruct subject's parent/legal guardian to record time of each instillation on the diary and to bring the diary and study drug (both bottles) to their next visit. Remind subjects that no other information should be recorded in the diary
- dispense new diary
- the unmasked designee must redispense study drug
- instruct subject's parent/legal guardian to continue dosing the study drug QID, at approximately four hour intervals for the next 2 weeks

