5.4.1 Permitted Therapy

Permitted therapy applies to the subject, breastfeeding mother, or wet nurse. Use of topical antibiotics is allowed if they are not used in combination with any steroid in the study eye (eg, Zylet® or TobraDex should not be used). Topical antibiotics used preoperatively and postoperatively are allowed bilaterally and must be recorded in the Concomitant Medications eCRF provided by the Sponsor. Intraoperative use of topical antibiotics or other standard of care surgical medications should be recorded in the source documentation only.

In the event that the subject requires surgery on the contralateral eye at any time during the study, the fellow eye will be treated at the Investigator's discretion with standard of care medication. The standard of care medication must be recorded under concomitant medications in the eCRF provided by the sponsor.

With the exception of the disallowed medications in Section 5.4.2, any medications that, in the Investigator's judgment, will not interfere with the study parameters are allowed to be used concurrently by the subject, breastfeeding mother, or wet nurse; for example, the following medications are permitted:

- systemic analgesics (eg, acetaminophen/paracetamol)
- oral birth control pills
- ≤100 mg/day acetylsalicylic acid (for breastfeeding mother/wet nurse only)
- hypoglycemic agents
- anticholesterol medications
- insulin
- systemic antimicrobials
- antidepressants
- thyroid preparations
- antihypertensive agents
- cardiovascular agents

- Standard anesthetic and mydriatic agents may be used intraoperatively or for postoperative diagnostic purposes (ie, IOP and funduscopy). Ocular NSAIDs may not be used for mydriasis or at any other time point during the study in the study eye. Ocular therapy with NSAIDs and/or corticosteroids in the fellow eye is permitted.
- The long term use of systemic NSAIDs is not allowed during the study. If unavoidable, use of systemic NSAIDs can be permitted only after Visit 5, but should be kept to a minimum and treatment duration with NSAIDs should be kept short (for example, one day per treatment period).
- Topical ocular hypotensive agents, if used at the end of surgery by the study site, will be used with ALL subjects treated at that site.
- Intracameral injection of antibiotic is allowed at the end of surgery.

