- the proportion of subjects with presence/absence and total number, if present, of precipitates on the implant and cornea at each visit (Postoperative Days 7, 14, and 28)

For each of the above endpoints, treatment groups will be compared using the Pearson Chi-squared test or fisher's exact test as appropriate. Differences between the proportions of treatment groups and 95% confidence interval about the differences will be presented.

Subgroup analyses will be performed for anterior chamber inflammation, anterior chamber cells, and anterior chamber flare as appropriate by method of assessment (slit lamp versus penlight with handheld magnifying 20 diopter lens), country (region), age group, IOL implantation, and iris color.

All subjects in the safety set will be included in the safety analyses. Intraocular pressure will be summarized by visit using continuous summaries (including change from baseline and change from screening) for the following items:

- change in IOP from baseline (Visit 2, Surgery/Randomization) to each visit
- greatest IOP change from baseline - including the measurement at Visit 3 (Postoperative Day 1)
- greatest IOP change from baseline - excluding the measurement at Visit 3 (Postoperative Day 1)
- ocular signs (biomicroscopic examination of the lids, conjunctiva, cornea, anterior chamber without pupil dilation)

Treatment emergent systemic AEs will be summarized using discrete summaries at the subject and event level by system organ class and preferred term for each treatment group. Treatment emergent ocular AEs will be summarized for treated eyes and fellow eyes separately. Similarly, treatment emergent AEs will be summarized by severity and relationship separately. All AEs will be coded using a MedDRA dictionary (the most current version available at the start of the study will be used).

Ocular symptoms will be summarized using discrete summary statistics by visit and treatment group. These data will be summarized under the safety analyses.

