6.2 Handling of Missing Data

For the primary efficacy endpoint analyzed using the ITT population, missing data and data from subjects placed on rescue medication prior to Day 14 will be analyzed using

the last observation carried forward (LOCF). For the PP analysis, missing data and data from subjects placed on rescue medication will not be imputed.

Data from unscheduled/repeated visits will be presented in listings and will be included in safety summaries for considering the worst-case scenario.

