10.4.3.3 Intraocular Pressure

Intraocular pressure (IOP) will be summarized at each visit and worst case on treatment for each subject using both continuous summaries (including change from baseline) and discrete summaries. Discrete summaries will include:

- Change in IOP from baseline (Visit 2) to each visit
- The proportion of subjects with change in IOP from baseline ≥ 5 and ≥ 10 mm Hg
- The proportion of subjects with treatment-emergent IOP ≥ 25 mm Hg
- IOP at each visit categorized into: ≤ 4 , 5 to 7, 8 to 12, 13 to 16, 17 to 20, 20 to 25, and ≥ 25
- Greatest IOP change from baseline - including the measurement at Visit 3 (Postoperative Day 1)
- Greatest IOP change from baseline - excluding the measurement at Visit 3 (Postoperative Day 1)
- Change from baseline in IOP at each visit categorized into: ≤ -5 , -4 to 0, 1 to 4, 5 to 9, 10 to 14, and ≥ 15

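### IOP summaries take no account of discretionary IOP-lowering treatment, so by-visit change and greatest change excluding Visit 3 can understate a difference between arms

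*Protocol*

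**What the plan says.** **Treatment of raised IOP.** A note in Protocol 5.1.3, worded to apply at any time point after surgery, says of raised IOP that "treatment or intervention is left to the Investigator's discretion and the subject is to continue the study". Protocol 5.4.1 separately covers "Topical ocular hypotensive agents, if used at the end of surgery by the study site"; a site that uses them must use them for all its subjects.

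**IOP analysis.** Protocol 7.1.3 and SAP 5.2.3 name three IOP endpoints: change from baseline to each visit, and greatest change with and without the Day 1 reading. SAP 10.4.3.3 states: "Intraocular pressure (IOP) will be summarized at each visit and worst case on treatment for each subject". Its list includes "Greatest IOP change from baseline - excluding the measurement at Visit 3 (Postoperative Day 1"), a companion maximum that keeps the Day 1 reading, "The proportion of subjects with change in IOP from baseline" of at least 5 and at least 10 mm Hg, and the proportion with treatment-emergent IOP of at least 25 mm Hg. Nothing in that section refers to IOP-lowering treatment.

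**Related rules.** In SAP 6.2, the missing-data and rescue rules concern efficacy, and rescue there is for inflammation. The same section says that unscheduled readings "will be included in safety summaries for considering the worst-case scenario". SAP 9.1 tabulates subjects by concomitant medication. SAP 10.4.2 only lists surgical procedures.

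**Screening.** Protocol 7.6.1 asks for IOP summaries "including change from baseline and change from screening". SAP 10.4.3.3 keeps only change from baseline. Neither SAP 6.3 nor the SAP revision history mentions the removal.

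**The concern.** Once a child has started IOP-lowering treatment, each later reading reflects the study steroid and that treatment together. If one steroid raises IOP more often, its arm is likely to receive more of this treatment, and the arms are drawn together in any table that uses later readings at face value.

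Two of the three named IOP endpoints are exposed. Change at each visit is affected from the first visit after treatment starts. Greatest change excluding Visit 3 is affected when a high Day 1 reading prompts treatment: the endpoint drops the reading that triggered treatment and keeps the treated ones.

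This matters because safety is part of the primary objective. The protocol's introduction also cites earlier studies of the LE suspension with fewer IOP rises of 10 mm Hg or more than prednisolone acetate, so readers will look closely at these tables.

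**Working it through.** **1. Figures in the documents.** There is no IOP sample size, SD or event rate to reproduce. The only power statement is for the inflammation endpoint: 60 per arm, SD 0.47, margin 0.35, two-sided alpha 0.05, 98% power. It reproduces (98.1% by noncentral t, 98.3% by normal approximation) but has no bearing on IOP.

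**2. Each planned summary after treatment starts.**

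| SAP 10.4.3.3 summary | Effect |
|---|---|
| Means, changes and categories by visit | Attenuated at every visit after treatment |
| Greatest change excluding Visit 3 | Loses the peak if treatment follows a high Day 1 reading; keeps it if the rise is first recorded later |
| Greatest change including Visit 3 | Keeps the peak recorded before treatment |
| Worst case; changes of 5 and 10 mm Hg; IOP of 25 mm Hg (not taken by visit) | Keep the peak recorded before treatment |

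**3. By-visit mean, illustration.** All inputs are assumed: responders 15% (prednisolone) and 5% (LE), rise 12 mm Hg, drop after treatment 6 or 12 mm Hg, treatment starting after the first elevated scheduled reading.

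Day 28 mean difference = (0.15 − 0.05) × (12 − share treated × drop).

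- None treated: 0.10 × 12 = 1.2 mm Hg.
- Half treated: 0.10 × (12 − 3) = 0.9, or 0.10 × (12 − 6) = 0.6.
- All treated: 0.10 × (12 − 6) = 0.6, or 0.10 × (12 − 12) = 0.0.

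**4. Greatest change, same inputs.** Add an assumed SD of change of 3 mm Hg and scheduled readings at Days 1, 7, 14 and 28. The table gives the excess, in percentage points (prednisolone minus LE), of subjects with a change of at least 10 mm Hg. It comes from a simulation of 400,000 subjects per arm; ranges with all treated cover drops of 6 and 12 mm Hg.

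| Onset of rises | Excluding Day 1: none treated | Excluding Day 1: all treated | Including Day 1: none treated | Including Day 1: all treated |
|---|---|---|---|---|
| All at Day 7 or 14 | 9.6 | 7.4-7.8 | 9.6 | 7.4-7.8 |
| Half at Day 1 | 9.6 | 3.7-5.2 | 9.7 | 7.5-8.0 |
| All at Day 1 | 9.9 | 0.0-2.4 | 10.0 | 7.6-8.1 |

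The last row can be checked by hand for a drop of 6 mm Hg. A single reading reaches 10 mm Hg with probability 0.7475 at a true rise of 12, 0.0912 at 6 and 0.0004 at 0.

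- Excluding Day 1: responders 1 − (1 − 0.0912)³ = 0.249; non-responders 0.001. Excess 0.10 × (0.249 − 0.001) = 2.5 points (simulated 2.4).
- Including Day 1: responders 1 − (1 − 0.7475)(1 − 0.0912)³ = 0.810; non-responders 0.002. Excess 0.10 × (0.810 − 0.002) = 8.1 points (simulated 8.1).

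**5. Precision.** With 70 per arm and an assumed SD of change of 3 to 4 mm Hg, the 95% interval for a difference in means has half-width 1.96 × SD × √(2/70), or 1.0 to 1.3 mm Hg.

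**The case against.** **Most peaks are kept.** A child with a 10 mm Hg rise on Day 1 who is then treated still counts in worst case, in greatest change including Visit 3, in the proportion with a change of at least 10 mm Hg, and in the 25 mm Hg proportion if that level is reached. Unscheduled readings add to worst case. This stands. What these summaries cannot show is a later rise suppressed by treatment begun on Day 1.

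**A tempting stronger reading.** A reader might infer that the plan hides steroid-related IOP differences. For example, suppose 10% and 2% of arms of 70 have a 10 mm Hg Day 1 rise that treatment fully reverses. The later mean difference of (0.10 − 0.02) × 10 = 0.8 mm Hg vanishes, and the count of rises of at least 10 mm Hg after Day 1 is 0 versus 0 instead of 7 versus 1.4. The documents do not support that conclusion. The example needs every rise on Day 1, every one treated, full reversal, and persistence if untreated. The planned threshold count is not limited to visits after Day 1, so it would still show 7 versus 1.4. Nor do the documents establish that a Day 1 rise, after only the first few doses, is caused by the steroid.

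**Drug use is tabulated.** SAP 9.1 counts subjects per medication, and SAP section 6 generally summarises by arm. An imbalance would be partly visible. But a per-medication count gives neither the number of subjects starting any such treatment nor the timing, and it is not linked to IOP.

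**IOP is descriptive.** No between-arm IOP test is stated, and summarising observed values is legitimate. An attenuation of 0.5 to 1.0 mm Hg could lie within sampling error (working, step 5). This limits the weight of the point but does not remove it, because descriptive tables are what readers will use to compare safety.

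**Conclusion.** The point holds as a limited attenuation. By-visit IOP summaries can understate a between-arm difference if IOP-lowering treatment is more common in one arm. Greatest change excluding Visit 3 can do so mainly when treatment follows a high Day 1 reading; if rises are first recorded at Day 7 or 14, it loses little. Greatest change including Visit 3, worst case and the threshold proportions keep most of the signal.

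The size cannot be derived from the documents: responder rates, size of rise, SD, share treated and response to treatment are all assumed above. Site-wide hypotensive use at the end of surgery does not differ by arm within a site, though it may lower early IOP in both arms. The efficacy hypothesis is unaffected. This is a worthwhile, inexpensive improvement to the safety analysis. The missing change-from-screening summary is a minor, separate inconsistency.

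**What to change.** In SAP 10.4.3.3:

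1. Report by arm the number, percentage and timing of subjects who first start IOP-lowering medication or intervention after the first dose, excluding site-wide end-of-surgery use. Add a composite of that start, or an IOP change of at least 10 mm Hg, or IOP of at least 25 mm Hg. Both thresholds are already in the SAP.
2. As a supportive table, repeat the by-visit and excluding-Visit-3 summaries with readings after the start of IOP-lowering treatment flagged or set aside. Do not carry the last pre-treatment value forward: that would put the Visit 3 reading back into an endpoint defined without it, and could stretch a one-day peak to Day 90.
3. Separately, restore the change-from-screening summary of Protocol 7.6.1 or record its removal in SAP 6.3.

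The cost is SAP wording and a few tables. The data are largely collected already: concomitant medications, surgical procedures and IOP. Exclusion criterion 2 bars children on IOP-lowering therapy at entry, so a start after the first dose is a new event. There are two limits. The composite needs a footnote because treatment is discretionary, and Protocol 5.4.1 has intraoperative medications recorded in source documents only, so site-wide use may have to be confirmed by site. No clinical rule changes.
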